## **8.0 STATISTICAL CONSIDERATIONS**

### **8.1 Statistical analysis plan**

Analysis will be done after all participants have completed the 12-week and 24-week timepoints, respectively. The interim analysis at 12-weeks will be for safety and efficacy of the intervention and will include a between group comparison of circulating biomarkers and a review of adverse events reported by study participants.

Statistical analysis will be performed using IBM SPSS 19.0 software. A 2 group analysis of variance (ANOVA) will be used to compare changes in biomarkers, physical function, body composition, body density, and quality of life between the exercise group and the WLC. Pearson's Product Moment Correlation will be used to measure associations between biomarkers in Aim 1 to body composition, body density, physical function and quality of life measured in aim 2. A value of  $p < 0.05$  will be considered statistically significant. The results of this study will be used to calculate power and determine sample size for future research questions in this field.

We will also evaluate the projects procedures and timeline for feasibility. We will document and review our timelines for recruitment for this pilot and ask participants to comment on their experiences in this project with pointed efforts to understand ways to improve the project procedures for effectiveness and efficiency. We will also assess feasibility by documenting and reviewing study patient description described below.

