### **3.3 Interim analysis**

Interim analysis will be performed once all participants have completed the 12th week of the project. This analysis will be done on the efficacy and safety of the intervention. We will do a between group comparison of circulating biomarkers and a review of adverse events (see section 8.1 for full analysis plan).

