### 7.3 Description by type of visit

7.3.1 Visit 1 (Baseline Visit) – This will be the first visit in this study and should last about 30-45 minutes. At this session, we will review the consent form, explain the purpose and procedures of the study, ask the subject to sign the consent form if you agree to participate in the study, and randomly assign the subject to one of the two groups mentioned above. Following this, the following things will happen:

1. Assignment of a Nike FitBit – Each participant, no matter which study arm, will be provided with a Nike Fitbit during the 6 month program. The FitBit will monitor activity and will assist the research team in tracking activity and sleep habits. We will instruct subjects on the use and care of the FitBit.
2. Blood Draw –15 mL of blood (two tubes or 1 tablespoon or 3 teaspoons) to measure circulating markers (PSA, PSMA, EPCA, uPA and uPAR) and circulating tumor cells.
3. Saliva Collection – we will collect about 4 mL of saliva (1/4 of a tablespoon or 3/4 teaspoon) to measure FBI concentrations in saliva.
4. Surveys for Quality of Life and Fatigue – subjects will be asked to complete 2 surveys that will take about 5 minutes to complete. These surveys are:
  - a. Health-Related Quality of Life (SF-36) – this survey will assess subject's overall health status, including physical functioning, role functioning, bodily pain, general health, vitality, social functioning, mental health and emotional health.
  - b. Functional Assessment of Chronic Illness – Fatigue (FACIT-F) – This survey evaluates the impact of fatigue in men with prostate cancer.

5. Body Composition, Body Mass Index and Body Density – will measure body fat percentage by measuring skinfold thickness at 3 sites (chest, abdomen, thigh). Body density will be measured using body fat percentage plus the addition of waist and arm circumference. Body mass index will be calculated by collecting by height and weight measurements from the subjects.
6. 6 minute walk test –overall physical function will be measured using the 6 minute walk test. We will track the distance traveled and use this as baseline score.

7.3.2 Visit 2 and Visit 3 (12 week and 18 week visit) – the following activities will be done at the 12 week and 18 week visit:

1. Blood Draw – we will collect 10 mL (2 teaspoons) to measure circulating markers (PSA, PSMA, EPCA, uPA and uPAR). Note: This is different than at baseline and final visit to quantify circulating tumor cells.

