2. Download FitBit Data – subjects will be asked to bring the FitBit to this visit so we can download the data that is on the FitBit.
3. Saliva Collection – we will collect about 4 mL of saliva (1/4 of a tablespoon or ¾ teaspoon) to measure FBI concentrations in saliva
4. Body Composition, Body Mass Index and Body Density – will measure body fat percentage by measuring skinfold thickness at 3 sites (chest, abdomen, thigh). We will also measure body mass index by collecting height and weight. Body density will be measured using body fat percentage plus the addition of waist and arm circumference.

7.3.3 Visit 4 (24 week visit; End of Study Visit) – the following activities will be done at the 24 weeks visit (or end of study visit)

1. Blood Draw – we will collect 15 mL of blood (two tubes or 1 tablespoon or 3 teaspoons) to measure circulating markers (PSA, PSMA, EPCA, uPA and uPAR) and circulating tumor cells.
2. Saliva Collection – we will collect about 4 mL of saliva (1/4 of a tablespoon or ¾ teaspoon) to measure FBI concentrations in saliva

3. Surveys for Quality of Life and Fatigue – subjects will be asked to complete 2 surveys that will take about 5 minutes to complete. These surveys are:
  - a. Health-Related Quality of Life (SF-36) – this survey will assess subject's overall health status, including physical functioning, role functioning, bodily pain, general health, vitality, social functioning, mental health and emotional health.
  - b. Functional Assessment of Chronic Illness – Fatigue (FACIT-F) – This survey evaluates the impact of fatigue in men with prostate cancer.
4. Body Composition, Body Mass Index and Body Density – will measure body fat percentage by measuring skinfold thickness at 3 sites (chest, abdomen, thigh). We will also measure body mass index by collecting height and weight. Body density will be measured using body fat percentage plus the addition of waist and arm circumference.
5. 6 minute walk test – we measure overall physical function by asking subjects to walk for 6 minutes. We will track the distance traveled and use this as the post-intervention score.
6. Return Nike FitBit – subjects will be asked to return the Nike FitBit to the research team. Data from the FitBit will be downloaded. After downloading, all data that is on the FitBit will be erased. A summary of the subject's activity can be provided if desired.

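### Section 8.1 does not say which visit the ANOVA of changes runs to, gives week-18 data no efficacy role, and would drop men without the endpoint visit despite section 8.4

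*Combined protocol and SAP*

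**What the plan says.** Section 7.3 schedules Visit 3 at week 18 with the same measurements as week 12: "the following activities will be done at the 12 week and 18 week visit". These are:

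- blood: "we will collect 10 mL (2 teaspoons) to measure circulating markers (PSA, PSMA, EPCA, uPA and uPAR";
- saliva for the fatigue index: "we will collect about 4 mL of saliva";
- body composition: "will measure body fat percentage by measuring skinfold thickness at 3 sites (chest, abdomen, thigh", with body mass index and body density.

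The 6-minute walk, the two surveys and circulating tumor cells are measured at baseline and week 24 only.

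Section 3.3 places the interim at week 12: "Interim analysis will be performed once all participants have completed the 12th week of the project". Section 8.1 gives the two analysis occasions: "Analysis will be done after all participants have completed the 12-week and 24-week timepoints, respectively". The between-arm method is one sentence: "A 2 group analysis of variance (ANOVA) will be used to compare changes in biomarkers" and in the other outcomes. It names no endpoint visit, visit term or baseline covariate. The threshold is p below 0.05.

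Section 8 never mentions week 18. Section 8.4 includes all randomised men in the primary analysis and says nothing more about missing values. Section 6.0 allows withdrawal at any time, does not replace those who leave, and asks staff to try to obtain the final visit from them.

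**The concern.** Three gaps meet in one sentence of section 8.1.

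1. **The endpoint visit is open.** Weeks 12, 18 and 24 could each supply the change. With five primary markers that makes 3 × 5 = 15 possible comparisons, each at p below 0.05. Week 24 is the natural choice for the final analysis, but the text does not fix it before the data are seen.
2. **Week 18 has no efficacy role.** Up to 30 men give blood and saliva at that visit, and no comparison is assigned to the results.
3. **The method cannot deliver section 8.4.** A two-group ANOVA of change needs both a baseline and an endpoint value. A man with weeks 12 and 18 but no week 24 falls out of a week-24 comparison, and no imputation is described that would keep him.

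At stake are a well-defined primary result and some precision in a trial of 15 men per arm.

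**Working it through.** The plan states no power, effect size, SD, dropout rate or visit correlation, so it has no figure to reproduce. Everything below uses unit SD and treats the covariance as known.

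**Inputs.** From section 4.1: 15 men per arm. Assumed: equal correlation r between all visits of 0.5 to 0.9, or correlation decaying over time at a = 0.7 to 0.95 per 6 weeks; 3 of 15 men per arm missing week 24, missing at random, with weeks 12 and 18 observed.

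**Step 1: week 18 with complete data.** With an arm-by-visit term and nobody missing, the week-24 estimate is the difference in week-24 means, so other visits do not alter it. For change scores at r = 0.8, the variance per man is 2(1 − 0.8) = 0.40 and the SE is √(2 × 0.40/15) = 0.231, with or without week 18. The gain is zero.

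**Step 2: baseline covariate in place of change scores.** The variance per man is 2(1 − r) for a change score and 1 − r² after adjustment. The ratio is (1 + r)/2, where r is the baseline-to-week-24 correlation.

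| r | change | adjusted | reduction |
|---|---|---|---|
| 0.5 | 1.00 | 0.75 | 25% |
| 0.8 | 0.40 | 0.36 | 10% |
| 0.9 | 0.20 | 0.19 | 5% |

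Under decay, r is a⁴: 0.240 at a = 0.7 and 0.815 at a = 0.95, giving reductions of 38% and 9%.

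**Step 3: using weeks 12 and 18 when week 24 is missing.** Relative to completers only, and with baseline adjusted in both, the variance falls by (3/15) × R². Here R² is the share of week-24 variance that weeks 12 and 18 explain, given baseline.

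- *Equal correlation.* With p = r/(1 + r), R² = 2p²/(1 + p). At r = 0.5, p = 0.333, R² = 0.167 and the reduction is 3.3%. At r = 0.9, p = 0.474, R² = 0.304 and the reduction is 6.1%. With week 12 alone, R² = p² and the reductions are 2.2% and 4.5%.
- *Decay.* R² = 1 − (1 − a²)/(1 − a⁸). At a = 0.7, R² = 1 − 0.510/0.942 = 0.459 and the reduction is 9.2%. At a = 0.95, R² = 1 − 0.0975/0.3366 = 0.710 and the reduction is 14.2%. With week 12 alone, R² = a⁴/(1 + a⁴) and the reductions are 3.9% and 9.0%.

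So weeks 12 and 18 together give about 3% to 14%. Week 18 accounts for roughly 1 to 2 percentage points under equal correlation and about 5 under decay.

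**Step 4: scale.** Losing 3 of 15 men per arm raises the variance by 15/12 = 1.25. With weeks 12 and 18 in the model this becomes 1.25 × 0.967 = 1.21 down to 1.25 × 0.858 = 1.07. The loss is reduced, not removed.

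**The case against.** **The timing sentence.** A reader might infer that the plan analyses only weeks 12 and 24 and throws week 18 away. The documents do not support that. The sentence in section 8.1 says when analyses are run, not which visits enter them, and an analysis run after week 24 could include week 18. Under section 8.2, completed week-18 assessments also count towards retention. What stands is that week 18 has no stated efficacy role.

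**Precision.** A reader might also infer a large loss of precision. Averaging all three visits with baseline adjustment gives a variance factor of (1 + 2r)/3 − r², against (1 + r)/2 − r² for weeks 12 and 24 and 1 − r² for week 24 alone. At r = 0.5 these are 0.417, 0.500 and 0.750; at r = 0.8 they are 0.227, 0.260 and 0.360. The implied cuts are 13% to 17% and 37% to 44%. They should not be claimed here. They belong to a time-averaged estimand, not the week-24 contrast, and to equal correlation. With decay at 0.8 per 6 weeks, adding week 18 to the average of weeks 12 and 24 gives a variance ratio of 1.03, which is no gain.

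**Dropouts.** It would be too strong to call week 18 the only way for an early leaver to contribute. Section 6.0 seeks a final visit from men who withdraw, the week-12 value carries information, and imputation is another route. Section 8.4 names no timepoint either. But a final visit that is only attempted will sometimes fail, and nothing is specified for that case.

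**A pilot.** The study gathers preliminary data to size later work and makes no power claim, so choosing a mixed model is partly preference. That limits the weight of the point. It does not excuse an undefined endpoint visit or a method that cannot meet section 8.4.

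**Conclusion.** The point holds as a gap in specification with a better method at hand. The endpoint visit for the changes is unnamed, week 18 has no efficacy role, and the ANOVA cannot include men who lack the endpoint visit, contrary to section 8.4. These three findings rest on the text alone.

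The size of the gain rests on assumptions. The baseline covariate gives 10% to 25% lower week-24 variance than change scores at equal correlation 0.8 to 0.5, and is the main source of gain over that range. At a correlation of 0.9 it gives 5%, about the same as the partial follow-up data. Weeks 12 and 18 add about 3% to 14% only if week-24 values are missing, at the assumed 3 of 15 per arm and missing at random. The known-covariance formulas slightly flatter the model in 30 men.

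The point is confined to serum markers, saliva and body composition. It does not reach the walk test, the surveys or circulating tumor cells, which are not measured at week 18.

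**What to change.** In section 8.1, for each serum marker, saliva and body composition, replace the ANOVA of changes with a mixed model for repeated measures. The outcomes are the values at weeks 12, 18 and 24; the terms are arm, visit, arm-by-visit and baseline value. Include all randomised men with any post-baseline value and name the week-24 arm contrast as primary.

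State the covariance structure and a small-sample degrees-of-freedom method in advance, and check that the named SPSS release fits them.

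In section 8.4, say that the model assumes missing at random and that men with no post-baseline value still do not contribute. Report their number by arm.

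The cost is SAP wording, a slightly more complex model in a 30-man pilot, and reliance on missing at random. No visit, sample or measurement changes.

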## **4.0 SELECTION OF PATIENT**

### **4.1 Number of patients planned**

This study plans to enroll 30 men with prostate cancer under active surveillance with 15 men in each arm.

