### **8.4 Handling of dropouts or missing data**

All randomized patients will be included in the primary analysis.

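### Section 8.1 compares changes by a two-group ANOVA with no baseline covariate: valid, but less efficient than ANCOVA unless the slope on the Visit 1 value is close to 1

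*Combined protocol and SAP*

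**What the plan says.** Section 8.1 gives the comparison in one sentence: "A 2 group analysis of variance (ANOVA) will be used to compare changes in biomarkers, physical function, body composition, body density". The sentence goes on to quality of life and names the exercise and wait-list arms. No covariate appears.

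The baseline of every listed outcome is collected at Visit 1 (Section 7.3.1). Blood is drawn "to measure circulating markers (PSA, PSMA, EPCA, uPA and uPAR) and circulating tumor cells", and for the 6-minute walk the plan says "We will track the distance traveled and use this as baseline score". Saliva, both surveys and the body measurements are also taken at that visit. All are repeated at Visit 4, at 24 weeks (Section 7.3.3).

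On size, Section 4.1 says "This study plans to enroll 30 men with prostate cancer under active surveillance with 15 men in each arm". Two analysis times are named in Section 8.1, 12 and 24 weeks. Section 3.3 limits the efficacy part of the first to the circulating biomarkers: "Interim analysis will be performed once all participants have completed the 12th week of the project". On the analysis set, Section 8.4 says only "All randomized patients will be included in the primary analysis".

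**The concern.** An ANOVA on changes is an ANCOVA with the baseline slope set to 1 instead of estimated. Nothing in the plan supports a slope of exactly 1 for outcomes as different as PSA, walking distance and SF-36 scores. Where the true slope is lower, the change score over-corrects chance baseline differences; where it is higher, it under-corrects them. Either way the between-arm comparison carries noise that the Visit 1 data could remove.

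Precision is at stake, not validity. It matters here because the arms are small and because Section 8.1 gives the trial a planning purpose: "The results of this study will be used to calculate power and determine sample size for future research questions in this field".

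**Working it through.** **Inputs from the plan.** N = 30, 15 per arm (Section 4.1); 1:1 allocation (Section 5.3); significance at p < 0.05 (Section 8.1; sidedness not stated, two-sided assumed).

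**Inputs the plan does not give.** SDs, the baseline to follow-up correlation ρ, the SD ratio k = SD(follow-up)/SD(baseline), effect sizes and a dropout rate. There is therefore no figure of the plan to reproduce, and every gain below rests on assumed values.

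**1. Variance per man, in units of the baseline variance.**
- Change score: 1 + k² − 2ρk
- ANCOVA residual: k²(1 − ρ²)
- Difference: (1 − ρk)², which is never negative and is zero only when the slope ρk equals 1.

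**2. Cost of estimating the slope.** In a given trial the ANCOVA variance is multiplied by 1 + t²/(N − 2), where t is the two-sample t statistic for the baseline difference. For a normal baseline the average of this factor is 1 + 1/(N − 4).
- All 30 men analysed: 1 + 1/26 = 1.0385, an average cost of about 3.8%. Simulation with 200,000 replicates gives 3.8% for a 15/15 split and for a 12/18 split (the example list in Section 5.3 has 12 control and 18 intervention codes).
- 24 men analysed: 1/20 = 5.0%. 20 men: 1/16 = 6.25%.
- Squared CI width at 30 men, counting the lost degree of freedom (28 to 27): 1.0385 × (2.0518/2.0484)² = 1.042, about 4.2%.
- Single trial at 30 men: the 95th percentile of t² on 28 degrees of freedom is 4.20, and 4.20/28 = 0.15, about 15%.

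**3. Average variance ratio, ANCOVA to change score, N = 30.** Ratio = k²(1 − ρ²)/(1 + k² − 2ρk) × 27/26.

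| k (assumed) | ρ = 0.5 | ρ = 0.7 | ρ = 0.9 |
|---|---|---|---|
| 1.0 | 0.779 | 0.883 | 0.987 |
| 0.8 | 0.593 | 0.652 | 0.631 |
| 1.2 | 0.904 | 1.003 | 1.015 |

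At k = 1 the ratio reduces to (1 + ρ)/2 × 27/26. The variance is thus about 22%, 12% and 1% lower, and the methods break even at ρ = 52/27 − 1 = 0.926. The other two rows show only how far the answer moves with k; the plan supports neither value.

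**4. Chance imbalance.** The standard error of the baseline difference between arms is √(1/15 + 1/15) = 0.365 baseline SD. For an imbalance d, the change-score difference is shifted by (ρk − 1)d. At k = 1 and ρ = 0.7, an imbalance of one standard error shifts it by 0.3 × 0.365 = 0.11 baseline SD in size. The shift averages to zero over randomisations, which is why the test is unbiased.

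**5. Power, for scale.** At k = 1, ρ = 0.7 and normal data, for assumed differences of 0.4, 0.6 and 0.8 baseline SD, power is 28, 54 and 78% for the change score and 31, 59 and 83% for ANCOVA.

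**The case against.** The planned test is common and valid, the study is a pilot with no power claim, and the documents supply nothing from which a gain can be computed. Section 4.2 admits any man aged 40 or over on active surveillance, so wide differences between men and a high correlation are plausible, and at equal SDs that is where the gain disappears. The residual SD and correlation needed for future planning can be computed whichever test is used. All of this stands, and it limits the point to efficiency.

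Four stronger readings might be inferred, and the documents do not support them:
- *The ANOVA on changes is biased or invalid.* With randomisation it is neither.
- *The 3.8% is a ceiling.* It is an average with all 30 men analysed. Section 6.0 says that men who discontinue are not replaced, and Section 8.4 gives no method for missing values, so fewer may contribute; one trial's realised cost can also be well above the average.
- *A gain of a third or more can be expected.* That needs a follow-up SD clearly below the baseline SD, for which the plan gives no basis.
- *The serum markers must be log-transformed.* The plan does not describe their distribution.

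One further limit applies to both methods. Section 7.3.1 places the Visit 1 measurements after assignment, so the baselines of self-reported and effort-dependent measures could be affected by knowledge of the arm. ANCOVA does not cure this, and the change score does not avoid it.

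**Conclusion.** The point holds as one of efficiency. Section 8.1 fixes the baseline slope at 1 without a stated reason, although the covariate is already collected for every outcome it lists. The trade-off favours ANCOVA: a small average cost when the slope is near 1, against a reduction in variance that grows as the slope moves away from 1. At equal SDs that reduction runs from about 22% to 1% over the assumed correlations of 0.5 to 0.9. These figures assume a normal baseline, one covariate and all 30 men analysed. The size of the gain for any outcome in this trial is unknown, and for a very stable marker it could be a slight loss. The change is worth making before data are seen, but the planned analysis would not mislead without it.

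**What to change.** Replace the ANOVA sentence in Section 8.1 with wording such as:

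> Each outcome listed in this section will be compared between the exercise and wait-list arms by ANCOVA of the follow-up value on arm and the Visit 1 value of the same measure. The final analysis uses the 24-week value. The 12-week interim comparison of circulating biomarkers uses the same model with the 12-week value. The adjusted difference between arms will be reported with its 95% confidence interval.

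This keeps the two analysis times the plan already names; any use of the 18-week values is a separate decision. The sponsor may keep change as the outcome, since with the Visit 1 value in the model the arm effect is the same. Reporting the residual SD and the baseline to follow-up correlation would serve the planned sample-size work.

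The change needs no new visits, samples or data. It uses one residual degree of freedom, with the variance cost set out above. It does not settle how men without a 24-week value enter the primary analysis under Section 8.4; the present ANOVA has the same gap. The report should also say that Visit 1 measurements followed assignment.

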## **2.0 STUDY OBJECTIVES**

**2.1 Primary Objective:** To demonstrate the impact of a home based exercise program versus wait-list control to modulate circulating prognostic biomarkers PSA, PSMA, EPCA, uPA and uPAR in men with prostate cancer under active surveillance..

2.1.1 Hypothesis: The home based exercise program participants will have significantly lower concentrations of circulating biomarkers compared to their non-exercising counterparts.

**2.2 Secondary Objective:** To determine the impact of a home based exercise program versus wait-list control to modulate a novel salivary biomarker for fatigue in men with prostate cancer under active surveillance.

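### Section 8.1 tests an unstated number of marker correlations at p<0.05 each, with no multiplicity control, exploratory label, time point or adjustment for arm

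*Combined protocol and SAP*

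**What the plan says.** Section 8.1 gives the Pearson analysis one sentence: "Product Moment Correlation will be used to measure associations between biomarkers in Aim 1 to body composition, body density, physical function". The same sentence adds quality of life as a fourth domain. The next sentence sets a single threshold for the whole section: a p-value below 0.05 "will be considered statistically significant".

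The Aim 1 markers are not listed in 8.1, and section 2.0 speaks of primary, secondary and other objectives rather than numbered aims. The natural match is the primary objective, which is to "modulate circulating prognostic biomarkers PSA, PSMA, EPCA, uPA and uPAR in men with prostate cancer" under active surveillance: five markers. The other side of each correlation is named only by domain.

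Section 8.1 is silent on:

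- the number of correlations;
- whether they use baseline values, later values or changes;
- whether the arms are pooled, separated or adjusted for;
- multiplicity;
- whether the results are exploratory.

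Section 8.4 says only that all randomised patients enter the primary analysis, which does not settle any of these.

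**The concern.** There are two separate problems.

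The first is multiplicity. Several markers crossed with several body, function and quality-of-life measures make a large grid of tests in 30 men. Each is judged at 0.05, and chance alone would be expected to produce some significant associations. Because the grid is not defined in advance, a reader of the results cannot tell how many tests stand behind those reported.

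The second is arm. Section 2.1.1 predicts that exercise lowers the markers, and section 2.3.1.1 predicts that it improves physical function and body composition. If both are true, post-baseline or change values pooled over the arms will be correlated even where the two variables are unrelated among men in the same arm. Such a correlation would repeat the between-group comparison and would not show a link between marker and fitness.

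What is at stake is the reading of a supporting analysis. Section 8.1 says that the results will inform power and sample size for later work, so a spurious link could influence what is studied next.

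**Working it through.** The plan states no number of correlations and no error rate for them, so there is no figure of its own to reproduce.

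**Inputs from the protocol**
- Markers: 5 (section 2.1). Circulating tumour cells are a possible sixth: the baseline and 24-week blood draws are taken "to measure circulating markers (PSA, PSMA, EPCA, uPA and uPAR) and circulating tumor cells" (section 7.3).
- Body measures: 3, namely body fat percentage, BMI and body density, listed in section 7.3 as "Body Composition, Body Mass Index and Body Density".
- Physical function: 1, the 6-minute walk (section 2.3.1).
- Quality of life: 8 SF-36 components plus FACIT-F (section 1.3).
- Sample size: 30, with 15 per arm (section 4.1).
- Threshold: 0.05, taken as two-sided because 8.1 does not say.

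**Number of tests**

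Measures: 3 + 1 + 8 + 1 = 13. Tests for one set of values: 5 × 13 = 65.

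Other readings of the same text:
- one score per named domain: 5 × 4 = 20;
- body fat, body density, 6-minute walk, one SF-36 total and FACIT-F: 5 × 5 = 25, or 5 × 6 = 30 with BMI;
- all scales without BMI: 5 × 12 = 60;
- with circulating tumour cells: 6 × 13 = 78;
- the 65 at both baseline and week 24: 130.

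**False positives if every null is true**

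Expected number = m × 0.05. This holds whether or not the tests are independent.
- m = 20: 1.0
- m = 30: 1.5
- m = 65: 3.25
- m = 130: 6.5

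Chance of at least one, if independent = 1 − 0.95^m.
- m = 20: 64%
- m = 30: 79%
- m = 65: 96%

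Independence is not realistic, since section 7.3 states "Body density will be measured using body fat percentage plus the addition of waist and arm circumference". A simulation of 65 null tests at n = 30 (20,000 runs) used assumed correlations among markers and among measures:
- 0.3 and 0.5: mean 3.25 false positives, 85% chance of at least one;
- 0.5 and 0.7: mean 3.30, 67% chance of at least one.

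**Size of correlation that counts**

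At n = 30 (28 df) the critical |r| = t/√(28 + t²) is 0.361 at the 0.05 level. With Bonferroni over 65 tests (0.05/65 = 0.00077) it would be 0.581.

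**Arm effect in pooled data**

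Assume 1:1 allocation, no association within either arm, and the same standardised arm shift d in both variables. The pooled correlation is then ρ = (d²/4)/(1 + d²/4). For example, d = 1.0 gives 0.25/1.25 = 0.20. Rejection rates at 0.05 were simulated with 15 men per arm:

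| d (SD) | pooled ρ | pooled test | adjusted for arm |
|---|---|---|---|
| 0.5 | 0.06 | 6% | about 5% |
| 0.8 | 0.14 | 11% | about 5% |
| 1.0 | 0.20 | 19% | about 5% |
| 1.2 | 0.26 | 31% | about 5% |

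The documents give no effect sizes, so the values of d are assumptions. The all-null scenario and the arm-shift scenario are separate, and their results should not be added.

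**The case against.** The strongest reply is that this is a small pilot gathering preliminary data, that the correlations match no objective in section 2.0, and that no trial conclusion rests on them. That is fair, and it limits the weight of the point. It does not dispose of it, because 8.1 applies the significance label without exempting the correlations.

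Four stronger readings are tempting, and the documents do not support them.

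- A reader might infer that the arms will be pooled. Pooling is the likely default from a single sentence that does not mention arm, but the plan does not say so.
- A reader might infer that some correlations will merely restate the arm effect. That needs pooled post-baseline or change values and sizeable shifts in both variables. At 0.5 SD the rate is close to nominal, and at baseline randomisation rules out a true arm effect. The supportable word is could.
- A reader might treat 65 as the plan's own number and 96% as the chance of a false finding. The first is a reconstruction, since 8.1 names four domains and not 13 measures. The second assumes independent tests.
- A reader might object that Pearson's r will be driven by a few high concentrations. The documents give no marker distribution and do not say whether values will be transformed, so this is only a general caution.

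It is also fair to say that a baseline association is a legitimate question and needs no adjustment for a treatment effect. The fix should leave that choice open.

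**Conclusion.** The concern holds in a limited form. Section 8.1 leaves the number, time point and arm handling of the correlations undefined, and judges each at 0.05 without multiplicity control or an exploratory label.

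The expected number of false associations is about 3.25 on the 65-test reading and 1.0 to 1.5 at 20 to 30 tests, in each case if every null is true. At 65 tests the chance of at least one is 96% under independence and about 67% to 85% under the assumed correlations.

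The arm problem is conditional on pooling and on post-baseline or change values. Given those, the excess over 5% is negligible at 0.5 SD and grows to about 31% at 1.2 SD. It matters most if the protocol's own hypotheses prove right. The point concerns a supporting analysis and leaves the primary between-group comparison untouched. It should still be corrected before analysis.

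**What to change.** In section 8.1:

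1. List the marker–measure pairs, state the resulting number of tests, and define Aim 1 and aim 2 in terms of the objectives in section 2.0.
2. State the time point, and whether levels or changes are correlated.
3. Adjust any correlation of post-baseline or change values for arm, by partial correlation.
4. Report estimates with 95% CIs as exploratory and make no claim from p<0.05. Alternatively, control the false discovery rate over the stated number of tests.
5. Optionally, add a rank-based or log-scale version as a sensitivity analysis.

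The cost is a change of wording and minor analysis work, with no new data, visits or patients. The downside is that fewer associations will be called significant.
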